9.4. Appendix D Imputation Rules for Missing AE dates

Imputation rules for missing or partial AE start dates and stop dates are defined below:

1. Missing or partial AE start date:

- If only DAY is missing, use the first day of the month, unless:
 - The AE end date is after the date of first vaccination or is missing AND the start month and year of the AE coincide with the start month and year of the first vaccination. In this case, use the date of first vaccination
- If DAY and Month are both missing, use the first day of the year, unless:
 - The AE end date is after the date of first vaccination or is missing AND the start year of the AE coincides with the start year of the first vaccination. In this case, use the date of first vaccination
- If DAY, Month and Year are all missing, the date will not be imputed. However, if the AE end date is prior to the date of first vaccination, then the AE will be considered a pre-treatment AE. Otherwise, the AE will be considered treatment-emergent.

2. Missing or partial AE end dates will not be imputed.

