-  All scheduled study visits should be completed within the defined visit window. Timing of Dose 3 is calculated in relation to Dose 1 (Day 1) and should not shift later than 167 days ( $\pm 7$  days) after Day 1; succeeding follow-up visits (Visits 10-17) are scheduled in relation to Dose 3. In the event the participant is not able to come on site for a clinic visit as a result of the COVID-19 pandemic (self-quarantine or disruption of clinical site activities following business continuity plans and/or local government mandates for “stay at home” or “shelter in place”), a safety call to the participant should be made in place of the clinic visit. The safety call should encompass all scheduled visit assessments that can be completed remotely, such as assessment for AEs and concomitant medications (eg, as defined in scheduled safety calls at Visits 12-15). Home visits will be permitted for all non-dosing visits in the event a participant cannot make it to the clinic as a result of the COVID-19 pandemic. Home visits must be permitted by the site IRB and the participant via informed consent and have prior approval from the Sponsor (or its designee).

-  In the event the visit for Dose 2 is disrupted and cannot be completed at Day 56  $\pm$  7 days as a result of the COVID-19 pandemic (COVID-19 vaccination under the FDA EUA or FDA approval, self-quarantine or disruption of clinical site activities following business continuity plans and/or local government mandates for “stay at home” or “shelter in place”), the window may be extended to Day 56 + 56 days (i.e., to 4 -months). When the extended window is utilized, the Day 84 visit is to be completed at 28 (-7 to +21) days after Dose 2 and monthly safety calls should occur every 28 days  $\pm$  7 days until the Month 6 visit (Day 168) for Dose 3. Dose 3 timing should continue to be based on Dose 1 and should not be adjusted if Dose 2 occurs in the extended dosing window (Dose 3 should not shift later than 167 days [ $\pm$  7 days] after Day 1); succeeding follow-up visits (Visits 10-17) are scheduled in relation to Dose 3.
-  Only documentation of COVID-19 vaccine is required.
-  Upon completion of final study procedures, including the final assessment and recording of MAAEs and SAEs, the participant’s treatment assignment may be unblinded via the IRT system.

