#### **4.1.2. Treatment Period**

All participants will receive vaccinations at Visits Day 1, Day 56, and Day 168.

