3.1. Primary Endpoints

The primary endpoints of the study are as follows:

- Solicited local and systemic adverse reactions (ARs) through 7 days after each vaccination.
- Unsolicited adverse events (AEs) through 28 days after each vaccination.
- Medically-attended adverse events (MAAEs) through 6 months after the last vaccination, and serious adverse events (SAEs) throughout the entire study period.
- Geometric mean titer (GMT) of serum neutralizing anti-CMV antibodies against epithelial cell infection and against fibroblast infection, and associated geometric mean ratio (GMR) of post-baseline/baseline titers at each timepoint.
- Proportion of participants with ≥ 2 -fold, 3-fold, and 4-fold increases in neutralizing antibody (nAb) over baseline against epithelial cell infection and against fibroblast infection at each timepoint.

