- c) study day after the date of the second vaccination but before the third vaccination (if applicable) will be calculated as: date of assessment/event – date of the second vaccination + 1; if study day is on the same day as the second vaccination, date and time will be compared with the second vaccination date and time. If it is prior to the second vaccination, then study day is calculated as [b\)](#); If it is after the second vaccination or the time is missing or not available, then study day is calculated as: date of assessment/event – date of the second vaccination + 1. If a subject did not receive the second vaccination, but received the third vaccination, study day after the second vaccination will be treated as missing, and only calculate in relative to the third vaccination.

- d) study day after the date of the third vaccination will be calculated as: date of assessment/event – date of the third vaccination + 1; if study day is on the same day as the third vaccination, date and time will be compared with the third vaccination date and time. If it is prior to the third vaccination, then study day is calculated as: date of assessment/event – date of the second vaccination + 1; If it is after the third vaccination or the time is missing or not available then study day is calculated as: date of assessment/event – date of the third vaccination + 1.

For GMT calculation, antibody values reported as below the lower limit of quantification (LLOQ) will be replaced by $0.5 \times \text{LLOQ}$. Values that are greater than the upper limit of quantification (ULOQ) will be converted to the ULOQ. Missing results will not be imputed.

The following **stages** are used for reporting and analysis purposes:

- Vaccination stage:

For assessments that will be collected throughout the study (eg, unsolicited AE), it consists first vaccination on Day 1 to the earliest date of (28 days after last vaccination [ie, the day of last vaccination and 27 subsequent days], discontinuation from the study, or death). If a subject receives three vaccinations, this stage starts at the first vaccination on Day 1 and continues through the earliest date of (28 days after 3rd vaccination, withdraw from study, or death).

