For assessments that will be collected at study visits (eg. laboratory and vital sign), if a subject receives three vaccinations, this stage starts at the first vaccination on Day 1 and continues through the earliest date of (Month 7 visit, withdraw from study, or death); If a subject receives first two vaccinations, this stage starts at the first vaccination on Day 1 and continues through the earliest date of (Month 3 visit, withdraw from study, or death); If a subject receives first vaccination only, this stage starts at the first vaccination on Day 1 and continues through the earliest date of (Month 1 visit, withdraw from study, or death).

- Follow up stage: For assessments that will be collected throughout the study (eg, unsolicited AE), this stage starts at 29 days after the last vaccination (ie, the day of last vaccination and 28 subsequent days, regardless of number of vaccinations received) and continue until the earliest date of (study completion, discontinuation from the study, or death).

There is no planned follow up stage for assessments that will be collected at study visits (eg. laboratory and vital sign).

- Overall stage: This stage starts at the first vaccination on Day 1 and continues through the earliest date of (study completion, discontinuation from the study, or death).
- 28 days after each vaccination stage: This stage starts at the day of each vaccination and continue through the earliest date of (the day of each vaccination and 27 subsequent days, next vaccination (if applicable)).

Unscheduled visits: Unscheduled visit measurements will be included in analysis as follows:

- In scheduled visit windows per specified visit windowing rules.
- In the derivation of baseline/last on-treatment measurements.
- In the derivation of maximum/minimum on-treatment values and maximum/minimum change from baseline values for safety analyses.
- In individual subject data listings as appropriate.

Visit windowing rules: The analysis visit windows for protocol-defined visits are provided in [Appendix B](#).

Incomplete/missing data:

- Imputation rules for missing prior/concomitant medications, non-study vaccinations and procedures are provided in [Appendix C](#).
- Imputation rules for missing AE dates are provided in [Appendix D](#).

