6.3.1. Adverse Events

An AE is defined as any untoward medical occurrence in a subject or clinical investigation subject who is administered a pharmaceutical product at any dose that does not necessarily have to have a causal relationship with the treatment.

A treatment-emergent AE (TEAE) is defined as any event not present before exposure to study vaccine or any event already present that worsens in intensity or frequency after exposure. Adverse events will also be evaluated by the investigator for the coexistence of medically-attended AE which is defined as an AE that leads to an unscheduled visit to a healthcare practitioner.

Unsolicited adverse events will be coded by PT and SOC using MedDRA and summarized by CMV serostatus (CMV-seropositive, CMV-seronegative and overall), vaccination group and stage (Vaccination Stage, Follow-up Stage, Overall Stage, and 28 days after each vaccination stage [including an overall summary, i.e., after any vaccination]; see [Section 6.1](#) for definitions of vaccination group and stage).

All summary tables (except for the overall summary of AEs) for unsolicited AEs will present SOC and PT, will include counts of subjects, and will be based on TEAEs. SOC will be displayed in internationally agreed order. PT will be displayed in descending order of frequency of total mRNA-1647 and then alphabetically within SOC.

Percentages will be based upon the number of subjects in the Safety Set within each vaccination group.

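### SAP Appendix D's missing-day rule protects only the first vaccination, so a day-missing AE in the month of dose 2 or 3 is usually dated outside the 28-day window it belongs to

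*SAP*

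**What the plan says.** SAP Appendix D opens its rule for partial AE start dates with "If only DAY is missing, use the first day of the month, unless". The exception that follows has two conditions: the AE ended after the first vaccination or has no end date, "AND the start month and year of the AE coincide with the start month and year of the first vaccination". The first-vaccination date is then used. Neither Appendix D nor SAP Section 6.1 mentions the months of the second and third vaccinations.

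The endpoint is defined dose by dose. SAP Section 3.1 lists as primary "Unsolicited adverse events (AEs) through 28 days after each vaccination". In SAP Section 6.1 the matching stage starts on each vaccination day, to "continue through the earliest date of (the day of each vaccination and 27 subsequent days, next vaccination (if applicable". SAP Section 6.3.1 tabulates unsolicited AEs by several stages, among them "28 days after each vaccination stage [including an overall summary, i.e., after any vaccination".

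One other stage matters here. For a participant with three doses, SAP Section 6.1 says of the Vaccination Stage that "this stage starts at the first vaccination on Day 1 and continues through the earliest date of (28 days after 3rd vaccination", so it has no gaps between doses. The dose days come from Protocol Section 4.1.2: "All participants will receive vaccinations at Visits Day 1, Day 56, and Day 168". If dose 2 is disrupted by the pandemic, Protocol Table 1 (footnote 14) says "the window may be extended to Day 56 + 56 days".

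**The concern.** The rule settles whether an event is treatment-emergent, and for that the first dose is the only reference needed. It does not settle which 28-day window the event belongs to in a three-dose trial. In the month of dose 1 a doubtful event is placed after the dose. In the month of dose 2 or 3 it is placed on the 1st, which almost always precedes the dose.

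What is at stake is the per-dose unsolicited-AE tables and the pooled summary after any vaccination. Events that truly followed dose 2 or 3 would tend to be missing from them, while those after dose 1 would be kept, so comparisons across doses would carry an artefact of date imputation. Appendix D exists because partial dates are foreseen. Protocol Section 8.9.1.3 also has reactions that were not captured in the eDiary and are reported verbally later entered as unsolicited AEs. It is an inference, not a stated fact, that such recalled events more often lack an exact day.

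**Working it through.** The plan gives no figure on this point, so there is none to reproduce. The check counts calendar dates.

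**Inputs**
- Doses at Days 1, 56 and 168, that is +0, +55 and +167 days (Protocol Section 4.1.2).
- Dose 2 within ±7 days, or as late as Day 112; dose 3 within ±7 days of Day 168, counted from dose 1 (Protocol Table 1 and its footnotes 13 and 14).
- Window: dose day plus 27 days (SAP Section 6.1).
- Assumptions: stage assigned by imputed start date; all 1,461 dose dates in a four-year cycle equally likely.

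**Formula.** For a dose on day m of the month, the imputed date lies m − 1 days before it. With a gap of G days since the previous dose, the imputed date is G − (m − 1) days after that dose. It falls in the previous dose's window when G − (m − 1) ≤ 27, that is m ≥ G − 26. If m = 1, the imputed date is the dose date and the placement is right. In all other cases the AE lies in no 28-day window.

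**Counts of dates in the cycle.** The 1st occurs 48 times (48/1,461 = 3.3%). Days 29, 30 and 31 occur 45, 44 and 28 times. Each of days 22 to 28 occurs 48 times.

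| Dose and timing | G | m needed for previous window | Previous window | No window |
|---|---|---|---|---|
| Dose 2, Day 56 | 55 | ≥ 29 | 117/1,461 = 8.0% | 1,296/1,461 = 88.7% |
| Dose 2, Day 49 | 48 | ≥ 22 | 453/1,461 = 31.0% | 960/1,461 = 65.7% |
| Dose 2, Day 63 | 62 | ≥ 36, impossible | 0% | 1,413/1,461 = 96.7% |
| Dose 3, Day 168, dose 2 at Day 56 | 112 | ≥ 86, impossible | 0% | 96.7% |
| Dose 3, Day 168, dose 2 at Day 112 | 56 | ≥ 30 | 72/1,461 = 4.9% | 1,341/1,461 = 91.8% |
| Dose 3, Day 161, dose 2 at Day 112 | 49 | ≥ 23 | 405/1,461 = 27.7% | 1,008/1,461 = 69.0% |

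In every row the imputed date precedes the dose for 96.7% of dose dates.

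**Weighting by true onset.** Assume onset is uniform over the 28 days after the dose. On average 15.6 of those 28 days lie in the dose's own month (15.58/28 = 55.6%). Of same-month AEs, 93.1% (dose 2) and 94.1% (dose 3) end in no window at the nominal schedule; the lowest scenario gives 83.6%. About 5.9% are kept in the right window. AEs that truly began in the window but in the following month are all kept, because the 1st of that month is then inside the window. So about 0.556 × 0.93 = 52% of all day-missing AEs in a dose-2 or dose-3 window would drop out of the 28-day tables.

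**Example.** Dose 1 on 20 January 2021 has a window to 16 February. Dose 2 on 16 March has a window to 12 April. An AE recorded as March 2021 is dated 1 March, which is in neither.

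**The case against.** Several points on the other side stand.

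- **The event is not removed from the analysis.** The Vaccination Stage and Overall Stage run without gaps from Day 1, unsolicited TEAEs are tabulated for both, and all are listed. Only the 28-day tables are affected.
- **The number affected may be small.** Protocol Section 8.9.2 asks for date and time of onset, visits 7 and 28 days after each dose record unsolicited AEs, and the analyses use cleaned data. The rule is the same for vaccine and placebo, and no hypothesis is tested.
- **Stage assignment by imputed date is not stated in the SAP.** It is the natural reading, but it is an assumption.

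Three stronger readings are tempting and are not supported.

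- A reader might infer that every such event is lost. A minority are dated in the previous dose's window, and about 3% of doses fall on the 1st.
- A reader might infer that the error runs only one way. For about 89% of dose dates the 1st of the month after the dose lies in that dose's window. A day-missing MAAE or SAE that truly began later in that month, after the window closed, is then moved in.
- A reader might infer that the rule for a missing day and month has the same gap. In the calendar year of dose 1 that rule uses the dose-1 date, which is inside a 28-day window. For an AE in the calendar year of the dose in question, the imputed date falls in some window for 92.6% of schedules (dose 2) and 69.6% (dose 3). The main fault there is attribution to dose 1.

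**Conclusion.** The point holds for day-missing start dates. Appendix D states a rule that suits treatment emergence but misplaces events relative to doses 2 and 3. Given stage assignment by imputed start date and evenly spread dose dates, a day-missing AE in a dose-2 or dose-3 month falls in no 28-day window for 88.7% and 96.7% of dose dates at the nominal schedule, and for 65.7% to 96.7% across the permitted windows. The remainder are the 3.3% of doses given on the 1st and, where the doses are close enough, dates in the previous dose's window. For true post-dose events the result is mostly loss from, or wrong attribution within, the tables that match the primary endpoint. These percentages apply only to events with a missing day. The documents give no count of those, so the absolute effect is unknown and may be slight.

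**What to change.** In Appendix D, for the rule where only the day is missing, extend the exception from the first vaccination to any study vaccination. If the AE start month and year match those of a study vaccination, and the AE end date is after that vaccination or missing, use that vaccination's date; otherwise use the 1st of the month. The rule is unambiguous: scheduled doses are at least 48 days apart (Day 49 − Day 1 = 48; Day 161 − Day 112 = 49), so no calendar month holds two.

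Leave the rule for a missing day and month unchanged. Choosing the latest compatible dose there would move AEs with no end date from dose 1 to the last dose of that year, which is a new misattribution.

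The cost is one sentence before final database lock. The change keeps all same-month AEs that began in the 28 days after the dose, against about 6% placed correctly now. In exchange, some AEs that began earlier in that month will be counted after the dose. A dose month holds on average 14.7 pre-dose days against 15.6 in-window post-dose days, so this is not negligible in principle. It is limited because unsolicited AEs other than MAAEs and SAEs are captured only through 28 days after each dose (Protocol Section 8.9.1.3), and because an end date on or before the dose excludes the event. It is the same conservative choice the SAP already makes for dose 1.

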9.5. Appendix E Schedule of Events

Please refer to Table 1 in Section 1.3 Schedule of Events, Table 6 and Table 7 in Appendix 2 Additional Schedule of Assessments in the protocol.

9.6. Appendix F Immunogenicity Assessments

The following laboratory assays are planned to measure the immune response to mRNA-1647 ([Table 3](#)):

- Functional (neutralizing) antibody titers against epithelial cell infection and against fibroblast infection will be measured by a neutralization assay.
- gB and Pentamer-binding antibody titers will be measured by ELISA.
- gB-specific IFN- γ secreting CD4 and CD8 T-cells will be determined by ICS.

- Pentamer-specific IFN- γ secreting CD4 and CD8 T-cells will be determined by ICS.

Table 3 Antibody-Mediated and Cell-Mediated Immunity Against Cytomegalovirus

Material	Component	Method	Unit
Serum	Neutralizing antibodies against epithelial cell infection and against fibroblast infection	Neutralization assay	Fold dilution (titer)
Serum	Anti-gB and anti-Pentamer antibodies	ELISA	Fold dilution (titer)
PBMC	gB and pentamer-specific CD4 and CD8 cytokine secreting T-cells	ICS	% cytokine secreting CD4 and CD8 T-cells

Abbreviations: ELISA, enzyme-linked immunosorbent assay; gB, glycoprotein B; ICS, intracellular cytokine staining; PBMC, peripheral blood mononuclear cell; Pentamer, gH/gL/UL128/UL130/UL131A glycoprotein complex.
